4.1 Impact of COVID-19

Due to pandemic COVID in year 2020, some extra analyses might be performed outside protocol specified analyses, if applicable.

Operational impact: Specified protocol deviation categories will be assigned to important deviations related to COVID-19 (e.g., treatment interruptions) and these will be summarized and listed separately. A summary table of the COVID-19 related deviations by relationship category will be provided.

Safety: To help the evaluation of the impact of the pandemic on safety, the incidence of COVID-19 related AE PTs will be presented incorporating any and all COVID-19 related AEs occurring before data cut-off. A listing of all COVID-related AEs will also be provided.

5 Appendix

5.1 Imputation rules

5.1.1 Study treatment

Patients with missing start dates are to be considered missing for all study treatment component related calculations and no imputation will be made. If start date is missing, then end-date should not be imputed.

Advanced Accelerator Applications,	Confidential	Page 24 of 27
A Novartis company		
SAP amendment		CAAA001A12401

5.1.2 AE and Concomitant medication (CM) date imputation

Any AEs and CMs with partial/missing dates will be displayed as such in the data listings.

Any AEs and CMs which are continuing as per data cut-off will be shown as 'ongoing' rather than the end date provided.

The imputations summarized in Table 5-1 and Table 5-2 are only used for analyses of time to and duration of AEs and concomitant medications

Table 5-1	Imputation of start dates (AE, CM) and assessments (LB, EG, VS)
-----------	---

Missing Element	Rule
day, month, and year	No imputation will be done for completely missing dates
day, month	If available year = year of study treatment start date, then
	 If stop date contains a full date and stop date is earlier than study treatment start date, then set start date = 01JanYYYY
	Else set start date = study treatment start date.
	 If available year > year of study treatment start date, then 01JanYYYY
	 If available year < year of study treatment start date, then 01JulYYYY
Day	 If available month and year = month and year of study treatment start date, then If stop date contains a full date and stop date is earlier than study treatment start date, then set start date= 01MONYYYY.
	• Else set start date = study treatment start date.
	 If available month and year > month and year of study treatment start date, then 01MONYYYY
	 If available month and year < month year of study treatment start date, then 15MONYYYY

Table 5-2Imputation of end dates (AE, CM)

Missing Element	Rule (*=last treatment date plus 30 days not > (death date, cut-off date, withdrawal of consent date))
day, month, and year	 Completely missing end dates (incl. ongoing events) will be imputed by the end date of the on-treatment period*
	• If start date is after last treatment date plus 30 days then impute to the earliest date between death date, cut-off date and withdrawal of consent date.
day, month	 If partial end date contains year only, set end date = earliest of 31DecYYYY or end date of the on-treatment period *
Day	If partial end date contains month and year, set end date = earliest of last day of the month or end date of the on-treatment period *

5.1.2.1 Prior therapies date imputation

Any prior anti-cancer therapies with partial/missing dates will be displayed as such in the data listings.

Advanced Accelerator Applications,	
A Novartis company	
SAP amendment	

Confidential

5.1.2.2 Post therapies date imputation

Not applicable.

5.1.2.3 Other imputations

Incomplete date of initial diagnosis of cancer and date of most recent recurrence

Missing day is defaulted to the 15th of the month and missing month and day is defaulted to 01-Jan.

5.2 AEs coding/grading

AEs are coded using the MedDRA terminology. The latest available MedDRA version at the time of the analyses should be used.

AEs will be assessed according to the CTCAE version 5.0 or more recent version.

The CTCAE represents a comprehensive grading system for reporting the acute and late effects of cancer treatments. The CTCAE grading is, by definition, a 5-point scale generally corresponding to mild, moderate, severe, life threatening, and death. This grading system inherently places a value on the importance of an event, although there is not necessarily proportionality among grades (a grade 2 is not necessarily twice as bad as a grade 1).

5.3 Laboratory parameters derivations

Grade categorization of lab values will be assigned programmatically as per National Cancer Institute (NCI) CTCAE version 5.0 or more recent version. The calculation of CTCAE grades will be based on the observed laboratory values only, clinical assessments will not be taken into account. The criteria to assign CTCAE grades are given in Novartis internal criteria for CTCAE grading of laboratory parameters. The latest available version of the document based on the underlying CTCAE version 5.0 or more recent version at the time of analysis will be used (refer to Table 5-3 in the Novartis internal criteria for CTCAE grading of laboratory parameters). For laboratory tests where grades are not defined by CTCAE v5.0 or more recent version, results will be graded by the low/normal/high classifications based on laboratory normal ranges.

A severity grade of 0 will be assigned for all non-missing lab values not graded as 1 or higher. Grade 5 will not be used. For laboratory tests that are graded for both low and high values, summaries will be done separately and labelled by direction, e.g., sodium will be summarized as hyponatremia and hypernatremia.

Imputation Rules

CTC grading for blood differentials is based on absolute values. However, this data may not be reported as absolute counts but rather as percentage of WBC.

If laboratory values are provided as '<X' (i.e. below limit of detection) or '>X', prior to conversion of laboratory values to SI unit, these numeric values are set to X.

Advanced Accelerator Applications,	Confidential	Page 26 of 27
A Novartis company		
SAP amendment		CAAA001A12401

The following rules will be applied to derive the WBC differential counts when only percentages are available for a xxx differential,

xxx count = (WBC count) * (xxx %value / 100)

Further derivation of laboratory parameters might be required for CTCAE grading. For instance, corrected calcium can be derived using the reported total calcium value and albumin at the same assessment using the following formula:

Corrected Calcium (mg/dL) = Calcium (mg/dL) - 0.8 [Albumin (g/dL)-4]

In order to apply the above formula, albumin values in g/L will be converted to g/dL by multiplying by 0.1), calcium values in mmol/L will be converted to mg/dL by dividing by 0.2495. For calculation of laboratory CTC grades 0 and 1, the normal range for derived corrected calcium is set to the same limits (in mg/dL) as for calculation.

CTC grades for the derived absolute WBC differential counts (neutrophils, lymphocytes) and corrected calcium will be assigned as described above for grading.

5.4 Statistical models

5.4.1 Analysis supporting primary objective(s)

Longitudinal data using mixed models will be preferably fitted on change from baseline (relative changes defined as the percent change of post-baseline value over baseline value, log2 transformation may be applied to the relative changes if distribution is right-skewed) with baseline (also log2 transform if distribution is right skewed), time (e.g. theoretical time since dosing) and the actual treatment volume by time interaction as fixed effect.

To account for correlated repeated measures within patients an unstructured variancecovariance matrix ('type=UN') will be used unless there is adequate justification in using an alternative variance-covariance matrix such as a power spatial covariance structure (type= 'sp(POW)') for unequally spaced data or a random subject effect.

Note: Although the unstructured covariance structure is the most robust variance-covariance matrix, in many cases, the number of parameters within the unstructured variance-covariance structure may cause your model to be unstable and thus a choice, such as the spatial covariance options, may provide a better fit to your data without having to fit so many parameters.

In SAS PROC MIXED, the repeated time effect should be explicitly included in the repeated statement. If this optional variable is not included, SAS assumes that the repeated measures data is similarly ordered for each subject. In addition, all missing response variables are indicated with periods in the input data set unless they all fall at the end of a subject's repeated response profile. Thus, as good standard practice we will include this repeated time effect explicitly. i.e **REPEATED** <**repeated-effect**></**options**>;

Relevant adjusted means and associated confidence intervals will be derived.

Standard model checking (e.g. residuals, random effects) will be performed to ensure that the basic assumptions of the model are not violated.

Advanced Accelerator Applications,	Confidential	Page 27 of 27
A Novartis company		
SAP amendment		CAAA001A12401

Alternative model making assumptions about the nature of the effects (e.g. linear effect of dose) may be investigated to better describe the changes observed.

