It has been shown that treatment with amino acid solutions, including LysaKare[®], could be associated with a risk of hyperkalemia. Increased serum potassium levels are generally transient and typically return to near baseline within 24 hours (Giovacchini 2011, Lapa 2014a, Lapa 2014b). Data reported on 2.5 % Lys-Arg solution (Krenning 2000) show that serum potassium levels gradually increased after the start of the infusion and reached a maximum between 2 and 4 hours. The increase in potassium levels was mild and did not manifest in any safety issues or clinically significant events. At 5 hours, the potassium levels appear to plateau/decrease and then decline back to baseline values.

No controlled clinical trials have been conducted with LysaKare[®] to assess its effect on serum potassium level. Therefore, there is a need to systematically assess the impact of LysaKare[®] on serum potassium levels in the GEP-NET patient population in a dedicated clinical trial.

Advanced Accelerator Applications Clinical Trial Protocol (Version 01)

Confidential

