2.5.5 Sensitivity analyses

The time course of the relative percent change from pre-dose to each time point will be tabulated. A Mixed Model Repeated Measures (MMRM) will be fitted to assess the whole-time course.

As a sensitivity analysis, a MMRM will be fitted with the relative percent change from pre-dose potassium value as dependent variable, and pre-dose potassium value, actual treatment volume, duration of infusion, timepoint, and actual treatment volume by timepoint interaction as covariates. This model implicitly imputes missing values by means of the estimated parameters and provides unbiased estimates for the data which are missing at random (MAR). Least-Squares Means and their 95% confidence intervals will be presented by timepoint and overall. A general (unstructured) variance-covariance matrix for the repeated measures for a single patient will be used.

This analysis will be repeated for absolute change from pre-dose.

Absolute change and relative percent change from pre-dose will be plotted against time to visualize the trend (increasing or decreasing) over time.

Advanced Accelerator Applications,	Confidential	Page 16 of 27
A Novartis company		
SAP amendment		CAAA001A12401

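### SAP 5.4.1 allows log2 of a percent change with no rule for values at or below zero; applied literally, records at or below baseline leave the relative-change MMRM (minor)

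*SAP*

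**What the plan says.** SAP 5.4.1 describes the longitudinal model. It takes relative change to be the "percent change of post-baseline value over baseline value, log2 transformation may be applied to the relative changes if distribution is right-skewed". The covariate is handled alike: the model is fitted "with baseline (also log2 transform if distribution is right skewed"). The section then states: "Relevant adjusted means and associated confidence intervals will be derived". It gives no offset, no rule for zero or negative values and no back-transformation, and it does not say how much skew triggers the option.

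SAP 2.5.5 fits the sensitivity MMRM "with the relative percent change from pre-dose potassium value as dependent variable", to describe the whole time course. It does not mention a transformation. It justifies the model under missing at random and adds: "This analysis will be repeated for absolute change from pre-dose".

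The time points are 2, 4, 6, 8, 12 and 24 h (SAP 1.2.1). Protocol 1.1 says that raised potassium levels "typically return to near baseline within 24 hours", and Protocol 4.1 repeats this. SAP 2.5.4 rules out replacement of missing data.

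**The concern.** A percent change is zero when potassium is unchanged and negative when it has fallen. Neither value has a logarithm, so software would set the transformed record to missing. The patient stays in the model through the other time points, but that record is gone, and it is gone because of the value it had. This is not missing at random, so the argument in 2.5.5 for unbiased estimates does not cover it.

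The expected return to near baseline puts the loss mostly at 24 h. The patients left at 24 h are those still above baseline. In addition, 2^x is positive for every x, so an LS mean and both its confidence limits, back-transformed to percent, lie above 0% whatever the data. On that scale the model could not show a return to baseline, which is part of the time course it is meant to describe.

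**Working it through.** **Inputs from the documents.** Mean baseline 4.2 mmol/L; mean change 0.6 at 2 h and 0.9 at 4 h; SD 0.3 at 4 h; minimum 25 evaluable patients (Protocol 12.8, SAP 3).

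**Assumed.** No document gives a mean or SD of change at 24 h. I take SD 0.3 and a 24 h mean m of 0 or 0.2 mmol/L. Since the option applies only under right skew, the main scenarios have skew 1 and 1.5.

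**The plan's own figure.** Half-width = t(0.975, n−1) × SD/√n. For n = 38 this is 0.0986 (the plan states 0.099). For n = 25 it is 0.1238, total length 0.248 (the plan states 0.25). These reproduce, but no figure in the documents concerns the log2 step.

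**Where log2 fails (baseline 4.2).**

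| Post-dose | Percent change | log2(percent change) | log2(post/pre) |
|---|---|---|---|
| 5.1 | +21.4% | 4.42 | 0.280 |
| 4.2 | 0% | minus infinity | 0 |
| 4.0 | −4.8% | undefined | −0.070 |

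**Share of 24 h records lost under right skew.** Let the change be m + G − kθ, with G gamma-distributed, shape k = 4/skew² and scale θ = 0.3/√k. The loss is P(G ≤ kθ − m).

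| Skew | k, θ, kθ | m = 0 | m = 0.2 |
|---|---|---|---|
| 1.0 | 4, 0.15, 0.60 | P(G ≤ 0.6) = 0.567 (14.2 of 25) | P(G ≤ 0.4) = 0.279 (7.0 of 25) |
| 1.5 | 1.78, 0.225, 0.40 | P(G ≤ 0.4) = 0.600 (15.0 of 25) | P(G ≤ 0.2) = 0.286 (7.2 of 25) |

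**Effect on the 24 h estimate.** At m = 0 the true geometric change is close to −½ × (0.3/4.2)² = −0.26%. The retained values alone back-transform to about 3.9% to 4.0%.

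The MMRM borrows from earlier time points and lowers this only partly. It was simulated with n = 25, unstructured covariance, pre-dose value and timepoint as covariates, and full infusions only. Assumed means were 0.6, 0.9, 0.7, 0.5, 0.3 and m at the six time points (only the first two are documented), with correlation 0.5 and baseline SD 0.4. There were 300 runs per scenario, and medians are given:

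- m = 0, skew 1 and 1.5: 3.2% and 3.4%, against a true change of about 0.
- m = 0.2, skew 1: 4.3%, against a true 4.6%.

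**Illustration only: normal changes.** The loss is Φ(−m/SD). With SD 0.3 it is 50%, 37%, 25% and 16% for m = 0, 0.1, 0.2 and 0.3. At 2 h it is Φ(−0.6/0.3) = 2.3% and at 4 h Φ(−0.9/0.3) = 0.1%, which shows that the loss sits at the late time points. Such data would rarely trigger the transformation: pooled skewness of the percent change was −0.07 to 0.14, and it exceeded 0.5 in only 0.3% to 3.6% of draws of 25 patients.

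**The case against.** **A ratio may have been meant.** Dividing the post-baseline value by baseline, with baseline also on the log2 scale, fits a log-ratio model. That is plausible, but 5.4.1 says percent change and 2.5.5 says it again, so a programmer who follows the text would transform the percent change. If a ratio was meant, the fix records the intent.

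**The option is only permissive.** This stands. 5.4.1 is an appendix that says the transformation may be used, and 2.5.5 names the untransformed percent change. A reader might infer that 24 h records will be lost from the planned analysis. The documents support only that they would be lost if the option is used literally.

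**Model checking would show it.** The SAP promises: "Standard model checking (e.g. residuals, random effects) will be performed". In the skewed scenarios log2 of the percent change has skewness of about −1.2 to −1.4 at 24 h, and more than half the 24 h records can be missing, so a failure may well be seen. But residuals exist only for retained records, and the section names no check of records used.

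**The size depends on assumptions.** This also stands. Near baseline does not mean at or below it, and the SAP states no back-transformation. The two scales also differ slightly even with almost no loss: at 4 h the simulated estimates, with normal changes, are 20.1% for log2 of the percent change and 21.3% for the log ratio. The simulation leaves out the volume and duration terms of 2.5.5.

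**Conclusion.** The rule in 5.4.1 is wrong as written: it permits a transformation that has no value for results the protocol expects at 24 h. If it is used literally under right skew 1 to 1.5 with a 24 h mean change of 0 and SD 0.3, about 57% to 60% of 24 h records are lost and the model shows a rise of roughly 3% where there is none. With a 24 h mean of 0.2 mmol/L about 28% are lost, but the estimate is almost right (4.3% against 4.6%).

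A reader might infer a general upward bias in the potassium results. The documents do not support that. The bias depends on the 24 h mean being very close to zero and on the option being taken up. The primary mean change with its 95% CI, the tabulated percent change and the absolute-change MMRM do not use the transformation, and the study tests no hypothesis. Severity is minor. That the rule is undefined is certain; the sizes rest on the assumed 24 h distribution.

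**What to change.** In SAP 5.4.1, replace log2 of the percent change by log2(post-dose/pre-dose) as the log-scale outcome. State that LS means and confidence limits are back-transformed as 100 × (2^x − 1). Add a cross-reference in 2.5.5. Every positive potassium value then has a defined outcome, and the result can be zero or negative.

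The cost is one sentence and a cross-reference, with no new data or patients. The downside is that potassium ratios lie close to 1, so the log ratio removes only part of any skew: a simulated 24 h skew of 1.0 becomes 0.8, and 1.5 becomes 1.2. The untransformed percent-change and absolute-change models already planned in 2.5.5 cover that case.

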5.4.2 Analysis supporting secondary objective(s)

Hyperkalemia and dose interruption/withdrawal events will be summarized in terms of percentage rates with 95% CIs. An exact binomial confidence interval (implemented using SAS procedure FREQ with EXACT statement for one-way tables) will be calculated (Clopper & Pearson, 1934)

SAS procedure FREQ will be used to estimate the proportion of subjects with hyperkalemia and dose interruption/withdrawal events (binary outcome = 1 or "Yes"), along with the associated 95% (=100 × (1 – *two-sided alpha level*)) two-sided Pearson-Clopper CI.

6 References

Clopper, C. J., & Pearson, E. S. (1934). The use of confidence or fiducial limits illustrated in the case of the binomial. Biometrical, 26, 404-413

Krenning, E. P., De Jong, M., & Valkema, R. (2000). Inhibition of renal uptake of radiomolecules with a combinaiton of lysine and arginine. European Patent Specification (EP 1 196 154 B1).
